1. STUDY SUMMARY

TITLE The use of soluble fibre for the prevention of gestational diabetes among high-risk women. A pilot study.

AIMS The primary aim of this study is to evaluate the effect of a soluble fibre supplement in the development of gestational diabetes in women at high-risk. The secondary aim will be to evaluate the effect of the soluble fibre supplement on glycaemic control in high-risk women who develop gestational diabetes in early pregnancy.

DESIGN We plan to conduct a randomised single-blinded controlled study to evaluate the effect of the consumption of soluble fibre, from early to mid-pregnancy, on the incidence of gestational diabetes, insulin sensitivity, insulin secretion and metabolic control in GDM diagnosed participants.

POPULATION We will be studying women with diagnosis of gestational diabetes in previous pregnancies, (considered as high-risk) aged >18 years.

ELIGIBILITY Women over 18 years old with a history of gestational diabetes in previous pregnancies will be eligible to apply to this study. After first assessment, eligible women will be split according to their glycaemic status in women with and without early gestational diabetes.

TREATMENT Participants in the treatment arms will be taking 5 gr of Guar gum fibre supplement with meals three times a day (total daily 15 g). Participants in the placebo arms will be taking 5 gr of Cellulose three times a day (total daily dose 15 g).

DURATION Participants will be involved for 12 weeks.

OUTCOME MEASURES

In women with normal glucose tolerance at first assessment:

Primary outcome: Gestational diabetes (yes/no) at 28 weeks gestation.

Secondary outcomes: Insulin sensitivity and insulin secretion at 28 weeks gestation.

In women with early gestational diabetes (diagnosed at first assessment):

Primary outcome: Glycaemic control assessed the need of insulin treatment (yes/no)

Secondary outcomes: In women requiring insulin treatment: days-to-insulin and total daily insulin dose.

INTRODUCTION

GESTATIONAL DIABETES

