5. RANDOMISED CONTROLLED STUDY

Aim: To evaluate the effect of a soluble fibre supplement in glucose metabolism in pregnant women at high risk of developing gestational diabetes.

Study methodology: 12 week randomised, placebo-controlled, single-blinded study.

Intervention: Women will first be categorised according to their glycaemic status into two groups: GDM and glucose tolerant women. Afterwards, each group will be randomised into two groups and given either

- 1) Fibre supplement (Guar gum)
- 2) Placebo (Cellulose)

The participants will take the dietary supplement three times a day for 12 weeks. They will receive regular antenatal control according to NICE guidelines recommendations. Compliance will be addressed by weekly phone calls.

Number of volunteers: The number of participants will be arbitrarily define as no data of this type of intervention exists in this cohort. 40 participants will be recruited. Previous studies, outside pregnancy, have observed metabolic effects in samples of 15-40 subjects.

Recruitment: Women will be recruited in the antenatal clinic at Queen Charlotte and Chelsea's Hospital. An information sheet will be provided to eligible women in the first antenatal visit to explain the purposes of the study. Women who decide to take part will be asked to sign a consent form.

Randomisation: Initially women will be categorised according to glycaemic status in two cohorts: **Glucose tolerant** and **Early gestational diabetes (GDM)** cohort. Each of the two cohorts will then be independently randomised to either intervention or standard care using the sealed envelope website. Guar gum (intervention) and cellulose (placebo) will be provided in identical packed sachets.

STUDY OUTCOME MEASURES

PRIMARY OUTCOME MEASURES

- Glucose values at 0 and 120 minutes during an OGTT performed at 28 weeks in the glucose tolerant group.
- Glycaemic control assessed by need of insulin treatment (yes/no), days to insulin treatment and total insulin dose.

SECONDARY OUTCOME MEASURES

Assessing insulin sensitivity and insulin secretion at 28 weeks of pregnancy in the glucose tolerant cohort of women through validated indices using glucose and insulin (or C-peptide) values derived from the OGTT.

- Insulin sensitivity will be assessed using the Matsuda formula (18).
- Insulin secretion will be assessed by second-void fasting UCPCR as described by McDonald et al (19).

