9. STATISTICS AND DATA ANALYSIS

Data handling and analysis will be carried out by SPSS version 20.0 version.

No power calculation to decide sample size will be used. The number of participants has been arbitrarily defined, as it is a pilot study. We aim to recruit 40 women.

Before randomisation, women will be categorised according to their glycaemic status in two cohorts: Glucose tolerant and GDM. Each of these two cohorts will be randomly allocated into the

intervention (soluble fibre supplement) and control (placebo) group. Randomisation will be by sealed envelopes. Participants but not researchers will be blinded as to the type of intervention prescribed.

Differences between group in each cohort will be assessed using Student t test or Mann-Whitney U test for numeric variables depending on distribution; χ^2 will be used for categorical variables.

In the Glucose tolerant women cohort:

For the primary outcome, GDM (yes/no), logistic regression analysis will be performed.

For the secondary outcomes, insulin sensitivity and insulin secretion, linear regression analysis will be performed.

In the early GDM cohort:

For the primary outcome, need for insulin treatment (yes/no), logistic regression analysis will be performed. Additionally days-to-treatment analysis will be performed for those participants starting insulin therapy during follow up.

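### Both binary primary outcomes rest on logistic regression at about 10 women per arm with no rule for an arm with no or all events, and the linear models name no baseline term

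*Combined protocol and SAP*

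**What the plan says.** Section 9 sets a total of 40 women without a power calculation. Women are first divided by early OGTT result into a glucose tolerant and an early GDM cohort, and each cohort is then randomised to two arms. Neither cohort sizes nor the allocation ratio are given.

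For the glucose tolerant cohort: "For the primary outcome, GDM (yes/no), logistic regression analysis will be performed". For the early GDM cohort: "For the primary outcome, need for insulin treatment (yes/no), logistic regression analysis will be performed". A general sentence on differences between groups in each cohort adds that "χ^2 will be used for categorical variables". No exact, penalised or other method is named in case a logistic fit fails.

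For the continuous outcomes: "For the secondary outcomes, insulin sensitivity and insulin secretion, linear regression analysis will be performed". No covariate is named. Section 6 provides for baseline sensitivity and secretion at the second visit, before randomisation, and for the same parameters at 28 weeks in the glucose tolerant cohort. Section 5 names the indices: the Matsuda formula for sensitivity, and for secretion, "Insulin secretion will be assessed by second-void fasting UCPCR".

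**The concern.** With so few women per arm, one arm may have no events or nothing but events. Logistic regression then has no finite estimate of the log odds ratio, and the standard error that software prints has no meaning. In a pilot, the estimate and its interval matter more than the p value, and they are what is lost. The failure is also most likely where it hurts most: when the supplement works well and its arm has no events. Without a rule set in advance, the replacement analysis would be chosen after the data are seen, by researchers who, under section 9, are not blinded.

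For the continuous outcomes, following section 9 literally sets aside a baseline value that the trial plans to obtain, and may give up precision that 20 women per cohort can ill afford.

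**Working it through.** **Inputs.** Total of 40 women, two cohorts, two arms (sections 5 and 9). The plan has no power, alpha or effect size to reproduce. Average per arm = 40 / (2 × 2) = 10, assuming even cohorts and 1:1 allocation. A cohort of 14 gives 7 per arm and leaves 26 for the other, or 13 per arm. The only related event rate is overall GDM recurrence of over 40% (Introduction). No rate is given for women who pass the early OGTT, nor for insulin need, so every risk below is an assumption.

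**Step 1: chance of an arm with no or all events.** For risk p and arm size n, a = pⁿ + (1 − p)ⁿ. For two arms, P = 1 − (1 − a₁)(1 − a₂). Example, 40% v 20% at n = 10: a₁ = 0.0062, a₂ = 0.1074, P = 1 − 0.9938 × 0.8926 = 0.113.

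| Placebo v supplement | 7 per arm | 10 per arm | 13 per arm |
|---|---|---|---|
| 40% v 40% | 6% | 1% | 0.3% |
| 40% v 30% | 11% | 3% | 1% |
| 40% v 20% | 23% | 11% | 6% |
| 30% v 15% | 38% | 22% | 13% |
| 20% v 20% | 38% | 20% | 11% |
| 40% v 10% | 49% | 35% | 26% |
| 20% v 10% | 59% | 42% | 30% |

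**Step 2: what the planned analyses give.** Take 0/10 on supplement v 5/10 on placebo. An ordinary logistic fit gave a log odds ratio of −22.6, standard error about 15,241 and Wald p = 0.999. Pearson chi-squared = 20 × (0 × 5 − 10 × 5)² / (10 × 10 × 5 × 15) = 6.67, p = 0.010. So two methods named in section 9 give opposite answers on one table. A profile-likelihood interval from the ordinary model still has a finite upper limit (odds ratio 0.29) but no lower limit above zero. At 0/10 v 0/10 chi-squared is undefined.

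**Step 3: an estimate that always exists.** Newcombe's interval for a risk difference combines the two Wilson intervals. For placebo 5/10 the Wilson limits are 0.237 and 0.763; for supplement 0/10 they are 0 and 0.278. Lower limit = 0.5 − √[(0.5 − 0.237)² + 0.278²] = 0.117. Upper limit = 0.5 + √[(0.763 − 0.5)² + 0²] = 0.763. So the difference is 50 points, interval 12 to 76. By the same method, 3/10 v 0/10 gives −4 to 60 points and 0/10 v 0/10 gives −28 to 28. The plan must say which result carries the conclusion, because the interval and chi-squared can also differ when arms are unequal: 3/9 v 0/11 gives −0.2 to 65 points, but chi-squared p = 0.038.

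**Step 4: baseline adjustment.** With N women and baseline correlation r, the variance of the adjusted arm difference relative to the unadjusted is about (1 − r²)(1 + 1/(N − 4)), where the second factor is the cost of estimating the covariate. The documents give no value of r.

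| r (assumed) | N = 20 | N = 14 |
|---|---|---|
| 0.4 | 0.84 × 1.0625 = 0.892 | 0.84 × 1.10 = 0.924 |
| 0.6 | 0.64 × 1.0625 = 0.680 | 0.64 × 1.10 = 0.704 |
| 0.7 | 0.51 × 1.0625 = 0.542 | 0.51 × 1.10 = 0.561 |

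Break-even is r = √(1/(N − 3)): 0.243 for N = 20 and 0.302 for N = 14. A simulation of 20,000 runs agreed to within 0.005.

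**The case against.** Four stronger readings are tempting, and the documents do not support them.

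- *The plan does not say which analysis is primary.* Section 9 gives chi-squared as a general comparison and then assigns logistic regression to each primary outcome by name. The natural reading is that logistic regression is primary. What is missing is a rule for when it fails.
- *No result would exist.* Section 9 does not commit to Wald intervals. Counts, the risk difference and a one-sided profile-likelihood limit survive. What is lost is the odds ratio and its Wald interval.
- *Failure is likely.* With both risks near 40%, it occurs in about 1% to 3% of trials at 10 per arm. The 35% and 42% figures need a large effect or low risks, and neither is in the documents. Against that, the glucose tolerant cohort excludes women already positive on the early OGTT, so its risk may be below the overall recurrence rate. Cohort size also depends on the OGTT results.
- *No secretion index is named.* Section 5 names fasting second-void UCPCR, and section 6 treats the 120-minute UCPCR as insulin response, a different quantity. For sensitivity, section 5 names the Matsuda formula, which is Equation 1 in section 6, although two modified equations are listed beside it.

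It is also fair to say that section 9 does not forbid covariates, that the gain from baseline adjustment rests on assumed correlations, and that one fallback sentence would meet the minimum need. Pilot status explains the absence of a power calculation. It does not explain a primary estimate that may fail with no stated alternative.

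**Conclusion.** The point holds in limited form. Followed literally, section 9 can leave either binary primary outcome without a usable odds ratio, and offers a second test that may contradict the logistic Wald result or be undefined. The chance ranges from about 1% to 42% at 10 per arm and from 6% to 59% at 7 per arm over the risks examined. It depends on assumed event rates, even cohorts and 1:1 allocation.

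Leaving out the baseline term forgoes a variance reduction of about 11%, 32% or 46% with 20 women at correlations of 0.4, 0.6 or 0.7. Below about 0.24, adjustment costs a little.

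The documents also disagree on what the primary outcomes are. The Study Summary has "Primary outcome: Gestational diabetes (yes/no) at 28 weeks gestation", while section 5 lists "Glucose values at 0 and 120 minutes during an OGTT performed at 28 weeks in the glucose tolerant group" and "Glycaemic control assessed by need of insulin treatment (yes/no), days to insulin treatment and total insulin dose". This must be reconciled with section 9, but it is a separate point and nothing above rests on it.

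**What to change.** **(a) Binary outcomes.** For GDM and for need for insulin, make the risk difference with a Newcombe 95% interval the main estimate, and state that this interval carries the conclusion. If an odds ratio is also reported, use Firth penalised logistic regression with a profile-likelihood interval and arm as the only term. For 0/10 v 5/10 this gives 0.05 (0.0003 to 0.55).

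**(b) Continuous outcomes.** Fit the 28-week index on arm and the second-visit value of the same index, with the scale (for example, log) fixed in advance. Use the indices that section 5 names: Equation 1 and fasting second-void UCPCR. The second-visit text in section 6 requests only serum C-peptide, while its Procedures text lists insulin as well. Reconcile these. If insulin is not assayed at the second visit, use Equation 2 at both visits.

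**Cost.** A few sentences in section 9. Newcombe coverage is approximate: over risks of 5% to 65% the lowest is 92.5% at 10 per arm and 91.1% at 7 per arm. At equal risks, non-coverage, which is the false-positive rate if the interval decides, reaches 7.7% at 8 per arm and 7.6% at 13 per arm. Newcombe limits can be worked by hand; Firth regression needs software beyond plain SPSS 20. Baseline adjustment uses one degree of freedom per model.

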- Women willing to participate in the study will be additionally requested to provide a second urine sample after the 120 min during the OGTT. When bloods are taken will also request HbA1c as part of the study's investigations.
- An OGTT to test for early GDM will be performed as part of routine care. During the OGTT blood samples are taken at 0 and 120 minutes. Additionally to glucose, which is normally measure during the OGTT, for study purposes we will request serum C-peptide at these time points.

Baseline insulin sensitivity and insulin secretion will be estimated through validated indices using serum glucose, insulin (or C-peptide) and urinary C-peptide.

After the participants have agreed to take part in the study and consent has been signed, data regarding anthropometrics, demographics and medical history will be collected. This information will be obtained by reviewing the participant's medical notes.

Anthropometric measurements will be recorded at the first antenatal routine visit, including: pre-pregnancy weight, weight at first visit and height. BMI will be calculated with this data.

Demographics, personal and medical history will be extracted from medical records, including: maternal age, ethnicity, education, smoking during pregnancy, medical history (hypertension, PCOS, other relevant condition), obstetric history (parity, stillbirth, macrosomia, pre-eclampsia).

3rd visit (Randomisation)

[figure not shown]
After obtaining the results from the OGTT, women will be categorised by their glycaemic status and divided into two independent cohorts:

- Women diagnosed with gestational diabetes (according to NICE guidelines 2015 diagnostic criteria): **early GDM** cohort
- Women with normal glucose tolerance or impaired glucose tolerance but not fulfilling GDM criteria: **Glucose tolerant** cohort.

Women from each cohort will be randomised into two groups after the results of the OGTT are obtained:

- Intervention group: Guar gum fibre supplement
- Placebo group: Cellulose supplement

Women will take the fibre supplement 3 times a day (with each main meal) until the 28th week of pregnancy when they will be re-evaluated.

4th visit (28th weeks gestation)

Glycaemic status will be assessed at 28 weeks gestation in the two cohorts of women participating in the study:

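### In the glucose tolerant cohort, Section 9 models glycaemia only as GDM yes/no and names no baseline-adjusted analysis of the fasting and 120-minute glucose values measured at both OGTTs

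*Combined protocol and SAP*

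**What the plan says.** Section 9 gives the glucose tolerant cohort two regression analyses. For glycaemia: "For the primary outcome, GDM (yes/no), logistic regression analysis will be performed". Linear regression is named only for the secondary outcomes, insulin sensitivity and insulin secretion. No covariates are listed for either. A general sentence in the same section compares numeric variables between arms, within each cohort, by Student t or Mann-Whitney.

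The sections differ on the primary outcome of this cohort. The Study Summary has "Primary outcome: Gestational diabetes (yes/no) at 28 weeks gestation". The fourth-visit text in Section 6 also takes the diagnosis of GDM as the endpoint. Section 5 lists instead "Glucose values at 0 and 120 minutes during an OGTT performed at 28 weeks in the glucose tolerant group".

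The entry values exist. For the entry test, Section 6 says "During the OGTT blood samples are taken at 0 and 120 minutes", and it repeats both time points for the 28-week test. GDM is diagnosed when either of two glucose cut-offs is exceeded (Section 6, Assessments), and women reach this cohort only by not meeting that definition at entry.

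On size, Section 9 says "We aim to recruit 40 women" and "No power calculation to decide sample size will be used".

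**The concern.** Cutting a measured glucose value at a diagnostic line discards how far each woman lies from it. Every woman in this cohort starts on the non-GDM side, so a change that leaves her there counts as nothing in the logistic model. The values are available at both visits, yet Section 9 names a regression for the secondary indices and none for glucose, which Section 5 calls primary.

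At stake is precision. With few women per arm, the one named glycaemic model uses the less informative form of the data, and no analysis is stated that uses each woman's own starting value. A pilot is read mainly for its estimates, and the plan does not commit to a baseline-adjusted glucose difference with a confidence interval.

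**Working it through.** **No figure to reproduce.** The plan gives 40 women without an effect size, SD, control rate, alpha or power.

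**Inputs**
- Total of 40 (Sections 5 and 9), two cohorts, two arms each. The cohort split and allocation ratio are not stated. Equal cohorts and 1:1 allocation give 40/4 = 10 per arm (assumed). If 40% or 60% of women are glucose tolerant, the figure is 8 or 12, before dropout.
- GDM rate at 28 weeks in this cohort: not given. The Introduction's recurrence rate of over 40% refers to later pregnancies in general, not to women who have passed an early OGTT. Range used: 10% to 40%.
- Correlation r between entry and 28-week glucose: not given. Range used: 0.3, 0.5, 0.7.
- Two-sided alpha 0.05, one normal glucose variable, equal SDs, one cut-off (all assumed; the real definition has two cut-offs).

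**Step 1. Information kept by yes/no.** Large-sample efficiency against an unadjusted comparison of the values is φ(z_p)² / [p(1−p)]. At p = 0.40, this is 0.386² / 0.24 = 0.62. Against a baseline-adjusted comparison, multiply by (1 − r²).

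| GDM rate | vs unadjusted | loss | vs adjusted, r = 0.5 | vs adjusted, r = 0.7 |
|---|---|---|---|---|
| 40% | 0.62 | 38% | 0.47 | 0.32 |
| 30% | 0.58 | 42% | 0.43 | 0.29 |
| 20% | 0.49 | 51% | 0.37 | 0.25 |
| 10% | 0.34 | 66% | 0.26 | 0.18 |

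**Step 2. Power at 10 per arm.** The shift in SD units is d = z(p0) − z(p1). For 40% to 20%: −0.253 − (−0.842) = 0.59. For 40% to 10%: −0.253 − (−1.282) = 1.03. Chi-square power is by exact enumeration without continuity correction. The t test uses the non-central t with non-centrality d√(n/2) and 18 df. The adjusted model replaces d by d/√(1 − r²) and has 17 df.

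| Fall in GDM | Chi-square | t test | Adjusted, r = 0.3 / 0.5 / 0.7 |
|---|---|---|---|
| 40% to 20% | 13% | 24% | 26% / 30% / 41% |
| 40% to 10% | 29% | 59% | 62% / 71% / 86% |

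The ordering does not depend on exactly 10 per arm. For 40% to 10%, chi-square, t test and adjusted (r = 0.5) power are 25%, 48% and 59% at 8 per arm, and 39%, 67% and 79% at 12.

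**Step 3. Effect of selection on r.** Entry to the cohort requires values below the cut-offs, which narrows the entry distribution and lowers r. As an illustration, take a bivariate normal with the top 40% of entry values removed. The entry variance falls to 0.42 of its full value, and r becomes r√0.42 / √(1 − r² + 0.42r²). Values of 0.3, 0.5 and 0.7 become about 0.20, 0.35 and 0.54. At r = 0.2, adjusted power for 40% to 20% is 24.5%, against 23.8% for the t test.

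**Step 4. Stability of the logistic estimate.** The odds ratio is not finite if an arm has no events or all events. At 10 per arm with 40% and 20%, the chance is 1 − (1 − 0.6¹⁰ − 0.4¹⁰)(1 − 0.8¹⁰ − 0.2¹⁰) = 11%. With 20% and 10% it is 42%. A linear model of glucose does not have this problem.

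**The case against.** The strongest reply is that the glucose values already have an analysis. They are numeric, and the general t test or Mann-Whitney sentence covers them. A reader might infer that the pilot would produce no usable estimate in mmol/L. The documents do not support that, since a t test compares means in mmol/L. For glucose itself, the gain from adjustment is therefore from 24% to 26%, 30% or 41%, not from 13%. This stands, and so does the point that selection below the cut-offs makes the higher correlations less likely.

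A reader might also infer that most of the information in the glucose values is lost. That is not general. Against the unadjusted comparison already planned, the loss is 38% at a 40% rate and passes one half only at about 20% or lower. Against an adjusted comparison it exceeds one half at all the rates considered if r is about 0.5 or more, but the documents supply neither figure.

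Third, GDM prevention is the stated aim, and the sample was not sized for power: "The number of participants has been arbitrarily defined, as it is a pilot study". Even the adjusted model would miss a 40% to 20% fall 59% to 74% of the time. Both points are fair. The first is a reason to keep GDM yes/no as the clinical outcome. The second means the sample size, not the model, is the main limit. Neither argues against estimating a glucose difference as precisely as the data allow.

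Finally, Section 9 lists no covariates for any regression, so non-use of the entry values is inferred from silence. That is why the point is put as no stated use.

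**Conclusion.** The point holds as a gap in pre-specification with a moderate cost in efficiency. Section 9 names one model for glycaemia in this cohort, on GDM yes/no, and leaves the glucose values to a general unadjusted test without stated use of the entry measurements. The yes/no form loses 38% to 66% of the information in an unadjusted comparison over GDM rates of 40% down to 10%, and more against an adjusted one. The further gain from adjusting, over the t test already planned, is between almost nothing and about 17 percentage points of power (41% − 24%) for a 40% to 20% fall, depending on r.

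These sizes rest on a single normal variable with one cut-off, 10 per arm, and rates and correlations that the documents do not give. They do not support replacing GDM yes/no with a glucose measure as the outcome from which the effect is read, which would be a change of estimand. Separately, the disagreement between the Study Summary, Section 6 and Section 9 on one side and Section 5 on the other needs settling. If Section 5's list is kept, Section 9's primary-outcome line must itself be rewritten.

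**What to change.** Add to Section 9, for the glucose tolerant cohort, a linear regression of 28-week 120-minute glucose on arm, with the same woman's entry OGTT value as covariate. Add a separate model of the same form for fasting glucose. Report each as a mean difference in mmol/L with a 95% CI.

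Present these alongside GDM yes/no, which stays as the clinical outcome, shown as counts per arm and a risk difference with CI. State one primary outcome for this cohort and make the Study Summary, Section 5, Section 6 (fourth visit) and Section 9 agree on it.

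The cost is analysis-plan wording and one further type of model, fitted twice. All the values are already collected at both visits, so no new samples, visits or participants are needed.
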